6.2 Secondary Endpoints

- 1. Improvement in oxygenation defined as any one of the following:
 - Stabilization of PaO2/FIO2 >250
 - Improvement in FIO2 by 50% or improvements ≥15% in S/F, P/F ratio from baseline at 12 hours, Day 5 and Day 10 (or end of treatment)
- 2. Improved clinical outcomes defined as one of more of the following:
 - Time to extubation following the site's extubation protocol

- Free from re-intubation
- Reduction in ICU days
- Reduction in the number of re-admissions to the ICU due to COVID-19 within 28 days
- Reduction in total hospital days
- Mortality [28 days] defined as Cardiopulmonary mortality from all causes

3. Safety and tolerability

 Monitoring of adverse events (AEs), serious adverse events (SAEs), chest CT or Chest X-rays, vital signs, ventilatory/oxygenation parameters, and laboratory tests.

6.3 Exploratory endpoints will include (where available as part of standard of care):

- Change in LDH
- Change in fibrinogen
- Change in WBC count including lymphocytes and neutrophil subsets
- Change in triglycerides
- Change in ferritin
- Change in CRP / ESR
- Change in IL-6
- Change in D-Dimer

Changes in these parameters will be assessed for each patient from baseline to end of study as well as changes between the active and control groups.

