2.1 Introduction

COVID-19 is a rapidly emerging pathogen that has recently been declared a pandemic by the World Health Organization (WHO). No targeted therapeutic treatments for coronavirus (COVID-19) have been identified. Symptoms range from mild upper respiratory tract infection to profound hypoxia, severe pneumonia, ARDS and death. Progression of end stage disease is unpredictable with high fatality rates in mechanically ventilated patients as a result of multi-organ failure. Among patients who require hospitalization, mortality may be 5% to 15%, and for those who become critically ill, reported mortality ranges from 22% to 62%.

Prostacyclin therapy—available in oral, inhaled, and intravenous forms—is an analogue which mimics endogenous prostacyclin (PGI2). Prostacyclin binds to its receptor (a G-protein coupled receptor) found on the surface of vascular smooth muscle and platelets, activates cyclic adenosine monophosphate (cAMP), and results in inhibition of platelet aggregation, vascular smooth muscle relaxation and vasodilation of the pulmonary arteries (Mitchell, Ali et al. 2008). Prostacyclins are most commonly used in the treatment of PAH due to their potent vasodilatory effects. In addition, prostacyclin analogs also inhibit platelet aggregation and may reduce prothrombotic effects of endothelin.

The rationale for use of vasodilators in COVID-19 patients rests on their rapid local effect on the pulmonary vasculature, which has shown to lead to increased oxygenation in other diseases, such as PAH (Higenbottam, Wheeldon et al. 1984) and post-surgical PH (De Wet, Affleck et al. 2004). Epoprostenol has the additional advantage over inhaled nitric oxide in that it may be directly administered through a standard ventilator (closed-circuit).

The rationale for aerosolized prostacyclin use in COVID-19 patients experiencing hypoxia leading to cardiac failure is two-fold:

- (1) inhaled prostacyclin therapy has been used in the treatment of ARDS and has been shown to improve oxygenation and ventilation-perfusion mismatch (see Section 9). Prostacyclins, such as epoprostenol, promote pulmonary vasodilation via a cyclic adenosine monophosphate-mediated decrease in intracellular calcium (Figure 4). While it has not been associated with improved outcomes, such as mortality, and it's use in ARDS is off-label, it may be used in severe life-threatening hypoxemia refractory to conventional ARDS management, such as has been seen in COVID-19.

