4.4.1 Criteria for Stopping VentaProst Treatment

Individual patients stopping criteria: At any time during study drug administration, patients may be removed from study treatment and placed on standard of care (SoC) therapy if they meet one or more of the following pre-defined criteria leading to a deterioration in their condition:

- Severe hypotension as evidenced by a systolic BP < 90 mmHg or MAP < 60 mmHG for >2 hours from the start of VentaProst
- Need for VV ECMO
- Need to increase existing vasopressor therapy by more than 25%
- Worsening oxygenation, ventilatory, or hemodynamic parameters that in the opinion of the investigator the patient should be removed from study treatment
- Massive hemoptysis thought to be clinically significant and not due to endotracheal tube trauma
- Pulmonary Edema

Study stopping criteria: If 3 patients are removed from the study for any of the above conditions, the study will stop further enrollment and investigation will be conducted to determine the cause of the events. An independent safety evaluation will also be conducted. If it is suspected that the investigational product has caused the events, the study will be terminated.

Independent Safety Evaluation: Independent safety evaluation will be conducted by a licensed physician who is not involved in the VentaProst COVID-19 clinical study or the sponsoring organization.

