5.6.1 Prohibited Concomitant Therapy

Other inhaled vasodilators.

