6. CRITERIA FOR EVALUATION

6.1 Primary Endpoint

- 1. Reduction of respiratory failure. Failure is defined by any one of the following:
 - Requires VV ECMO
 - Inability to extubate within 10 days or reintubation within < 24 hours
 - Change in S/F, oxygenation index and P/F ratio (≥15%) from baseline to 12 hours, Days 1, 2, 3, 4, 5, 6, 7, 8, 9 and Day 10 (or end of treatment)

or

- 2. Reduction of cardiac or circulatory failure. Failure is defined by any one of the following:
 - Need to begin inotropic therapy or 10% increase in current vasopressor therapy
 - Worsening hemodynamic parameters
 - Cardiac troponin >20% from baseline
 - BNP > 15% of baseline
 - Need for temporary mechanical circulatory support (IABP, Impella)
 - Requires VA ECMO

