10.6.2 Secondary Efficacy Endpoints

Key secondary endpoints include:

- 1. Improvement in oxygenation defined as any one of the following:
 - Stabilization of PaO2/FIO2 >250
 - Improvement in FIO2 by 50% or improvements ≥15% in S/F, P/F ratio from baseline at 12 hours, Day 5 and Day 10 (or end of treatment)
- 2. Improved clinical outcomes defined as one of more of the following:
 - Time to extubation following the site's extubation protocol
 - Free from reintubation
 - Reduction in ICU days
 - Reduction in the number of re-admissions to the ICU due to COVID-19 within 28 days
 - Reduction in total hospital days
 - Mortality [28 days] defined as Cardiopulmonary mortality from all causes
- 3. Safety
 - Monitoring of adverse events (AEs), serious adverse events (SAEs), chest CT or Chest X-rays, vital signs, ventilatory/oxygenation parameters, and laboratory tests.

10.6.3 Key Exploratory Endpoints include:

- Change in LDH
- Change in fibrinogen
- Change in WBC count including lymphocytes and neutrophil subsets
- Change in triglycerides
- Change in ferritin
- Change in CRP / ESR
- Change in IL-6
- Change in D-Dimer

Changes in these parameters will be assessed for each patient from baseline to end of study as well as changes between the active and control groups.

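### Oxygenation readings taken on ECMO are not excluded from the secondary endpoint, so a patient who fails the primary endpoint by ECMO can also be scored as improved

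*Combined protocol and SAP*

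**What the plan says.** All references are to the latest protocol version in the combined document.

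- **Secondary endpoint (Sections 6.2 and 10.6.2, synopsis).** The rule is "Improvement in oxygenation defined as any one of the following". One limb is a P/F ratio stabilised above 250, with no time point attached. The other is "Improvement in FIO2 by 50% or improvements ≥15% in S/F, P/F ratio from baseline at 12 hours, Day 5 and Day 10", where end of treatment can stand in for Day 10. Neither limb is conditioned on the support the patient was receiving.
- **Primary endpoint (Sections 6.1 and 10.6.1).** "Requires VV ECMO" is a respiratory failure, and VA ECMO is a circulatory failure.
- **Stopping study drug (Section 4.4.1).** Need for VV ECMO is listed, but the rule is permissive: "patients may be removed from study treatment and placed on standard of care (SoC) therapy". VA ECMO is not listed.
- **Schedule (Table 2).** Oxygenation and ventilator parameters are due at baseline, at 12 hours, and daily up to the column for Day 10 or end of study treatment.
- **Analysis (Sections 10.1 and 10.3, synopsis).** All available data enter and nothing is imputed. No SAP will be written. Efficacy is summarised as success or failure on any primary or secondary endpoint, with no order of precedence between them.
- **Other inhaled vasodilators (Section 5.6.1).** They are prohibited. The plan does not say how readings are scored if one is given.

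**The concern.** Ventilator FiO2, S/F and P/F are meant to show how well the patient's own lungs are working. On ECMO the circuit supplies oxygen and ventilator FiO2 can be reduced, so all three can improve because the patient needed ECMO. The primary endpoint treats that event as failure. The secondary endpoint, followed as written, can treat the readings it produces as success. The two endpoints would then contradict each other for the same patient, and the improvement rate would partly count how often ECMO was used. With 10 patients per arm, one or two such patients are enough to change the picture.

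**Working it through.** The plan gives no rate, effect size or power for this endpoint, so there is no figure to reproduce. The check is a reading of the rules plus illustrative arithmetic.

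**Step 1: can an on-ECMO reading reach the endpoint?**
- Section 4.2 excludes patients on ECMO, so ECMO can arise only after entry.
- If a patient stays on study drug after starting VV ECMO (Section 4.4.1 allows this) or VA ECMO (not named there), the Table 2 readings continue to Day 10.
- Section 10.3 takes all available readings, and Section 6.2 needs one limb. The patient is a primary failure under Section 6.1 and can be improved under Section 6.2.

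**Step 2: are the thresholds within reach?** Change is measured from baseline: S/F = SpO2 (%) / FiO2; S/F change = (S/F on ECMO / S/F at baseline) − 1; FiO2 fall = 1 − (FiO2 on ECMO / FiO2 at baseline). All readings are assumed. The on-ECMO reading is SpO2 92% on FiO2 0.5, so S/F = 92/0.5 = 184.

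| Assumed baseline | Baseline S/F | S/F change | FiO2 fall | Criteria met |
|---|---|---|---|---|
| SpO2 88%, FiO2 1.0 | 88 | 184/88 − 1 = +109% | 50% | both |
| SpO2 92%, FiO2 0.6 | 153 | 184/153 − 1 = +20% | 17% | S/F only |
| SpO2 92%, FiO2 0.5 | 184 | 0% | 0% | neither |

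The result depends on how ill the patient was at baseline. Misscoring is possible, not automatic.

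**Step 3: effect of one patient.** With 10 per arm, 1/10 = 10 percentage points. Starting from an assumed 7/10 Active and 3/10 Control, with Newcombe 95% intervals:

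| Scoring | Active vs Control | Difference | 95% CI | Fisher p |
|---|---|---|---|---|
| All readings | 7 vs 3 | 40 points | −3 to 67 | 0.18 |
| One Control patient rescored | 7 vs 2 | 50 points | 7 to 74 | 0.07 |
| One Active patient rescored | 6 vs 3 | 30 points | −12 to 60 | 0.37 |

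Section 10.3 judges significance by a 95% CI but does not name the method. On the Newcombe interval, rescoring one Control patient changes the conclusion; on Fisher's test it does not. The difference moves up or down according to the arm.

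**Step 4: how many patients?** The documents give no ECMO rate. Assume that 10% to 30% of patients start ECMO, that 50% to 100% of those have a qualifying reading on it, and that one time point is enough.
- Expected per arm: 10 × 0.10 × 0.5 = 0.5, up to 10 × 0.30 × 1.0 = 3.
- Chance of at least one among 20: 1 − 0.95^20 = 64%, up to 1 − 0.70^20 = 99.9%.

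**Step 5: any or all time points?** Section 6.2 joins 12 hours, Day 5 and Day 10 with 'and'. If all are required, a patient must already have improved at 12 hours, and a later on-ECMO reading cannot score alone. The counts in Step 4 then fall. The P/F limb carries no time points, so the strict reading does not close that route, although Table 2 schedules SpO2 and no arterial gas.

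**The case against.** The plan is silent on ECMO readings; it does not deliberately credit them. Section 9.1.2.4 heads the Day 2 to 10 assessments as on-drug, and the last time point can be end of treatment, so a patient taken off drug at ECMO may have no scheduled reading on it. Section 4.4 asks for end-of-treatment procedures from those who leave the study, which is not the same as leaving treatment under Section 4.4.1. This stands, and it reduces the number affected. It does not close the gap for patients kept on drug.

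This is also a secondary endpoint in an exploratory trial of about 20 patients with individual listings, and ECMO remains a primary failure. Using all readings regardless of ECMO is a legitimate estimand. That limits the importance of the point, but the plan never says that it has chosen that estimand.

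A reader might infer three stronger things that the documents do not support:

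- **That the error runs against the drug.** This needs more ECMO in Control, and no passage gives rates by arm.
- **That rescue inhaled vasodilators are a second route of the same kind.** Section 5.6.1 prohibits "Other inhaled vasodilators", and no passage describes them as rescue or as site standard care. The remark in Section 2.1 that "it may be used in severe life-threatening hypoxemia refractory to conventional ARDS management" is background on the drug class. What is missing is only a scoring rule should such a drug be given.
- **That a patient extubated by Day 10 after such a drug escapes the primary endpoint.** The daily oxygenation-change limb and the circulatory limbs of Section 6.1 could still apply.

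**Conclusion.** The point holds for ECMO. Followed as written, the plan allows a primary failure by VV or VA ECMO to be scored as improved on the secondary oxygenation endpoint. The size is 10 percentage points in that arm's rate for each affected patient. The number affected is unknown: the 0.5 to 3 per arm above rests entirely on assumed rates and on the any-one-time-point reading. Its upper end also sits badly with Section 4.4.1, under which three removals halt enrolment, so 10 per arm might not be reached. The direction of bias is not known; it flatters whichever arm has more ECMO. That ECMO lets ventilator FiO2 be reduced is a general clinical premise, not something the protocol states. The change is worth making because the contradiction sits in the scoring rule itself and no SAP will resolve it.

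**What to change.** In Sections 6.2 and 10.6.2 and the synopsis:

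1. Score any patient who has started VV or VA ECMO since randomisation as not improved at that and all later time points.
2. State whether improvement needs any one or all of 12 hours, Day 5 and Day 10 (or end of treatment). If any one is enough, say whether a gain at 12 hours before ECMO still counts.
3. Add a sensitivity analysis using all readings regardless of ECMO.
4. As a sensitivity analysis only, apply the same not-improved scoring from the start of a prohibited non-study inhaled vasodilator.

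Leave the primary endpoint unchanged; adding vasodilator use to it would be a redesign.

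The cost is a few sentences. ECMO must already be ascertained for the primary endpoint, and Section 5.6 already records medications and therapies. The small downside is that the endpoint becomes a composite of oxygenation and ECMO, which the all-readings analysis lets a reader separate. This is scoring only and changes nothing in patient care.

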 - Free from reintubation
 - Reduction in ICU days
 - Reduction in the number of re-admissions to the ICU due to COVID-19 within 28 days.
 - Reduction in hospital days Mortality (28 Days) defined as Cardiopulmonary mortality or mortality from all causes.
- 3. Safety and tolerability:
 - Monitoring of adverse events (AEs), serious adverse events (SAEs), chest CT or Chest X-rays, vital signs, ventilatory and oxygenation parameters, and laboratory tests.

Exploratory endpoints will include (where available as part of standard of care):

- 1. Change in LDH
- 2. Change in fibrinogen
- 3. Change in WBC count including lymphocytes and neutrophil subsets
- 4. Change in triglycerides
- 5. Change in ferritin
- 6. Change in CRP / ESR
- 7. Change in IL-6
- 8. Change in D-Dimer

Changes in these parameters will be assessed for each patient from baseline to end of study as well as changes between the active and control groups.

Ventilatory Parameters

OSU SOC:

Ventilator Type (GE)

Parameters to monitor are:

- 1. Ventilator Mode
- 2. FiO₂
- 3. Inspiratory Time
- 4. Mean Airway Pressure
- 5. Peak Inspiratory Pressure
- 6. Positive End Expiratory Pressure
- 7. Respiratory Rate
- 8. Tidal Volume

Criteria for Stopping VentaProst Treatment

Individual patients stopping criteria: At any time during study drug administration, patients may be removed from study treatment and placed on standard of care (SoC) therapy if they meet one or more of the following pre-defined criteria leading to a deterioration in their condition:

- Severe hypotension as evidenced by a systolic BP < 90 mmHg or MAP < 60 mmHG for >2 hours from the start of VentaProst
- Need for VV ECMO
- Need to increase existing vasopressor therapy by more than 25%

	 Worsening in oxygenation, ventilatory, or hemodynamic parameters that in the opinion of the investigator the patient should be removed from study treatment Massive hemoptysis thought to be clinically significant and not related to endotracheal tube trauma Pulmonary edema
	Study stopping criteria: If 3 patients are removed from the study for any of the above conditions, the study will stop further enrollment and an investigation will be conducted to determine the cause of the events. An independent safety evaluation will also be conducted. If it is suspected that the investigational product has caused the events, the study will be terminated.

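### Five of the six secondary clinical-outcome items do not say how death counts, any one item is enough, and mortality is worded two ways

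*Combined protocol and SAP*

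**What the plan says.** All references are to the current (last) protocol version in the file.

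Sections 6.2 and 10.6.2 introduce the clinical group of secondary endpoints with "Improved clinical outcomes defined as one of more of the following", evidently meaning one or more. The six items are:

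1. "Time to extubation following the site's extubation protocol"
2. "Free from re-intubation"
3. "Reduction in ICU days"
4. "Reduction in the number of re-admissions to the ICU due to COVID-19 within 28 days"
5. "Reduction in total hospital days"
6. "Mortality [28 days] defined as Cardiopulmonary mortality from all causes"

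The synopsis words the sixth item differently: "Mortality (28 Days) defined as Cardiopulmonary mortality or mortality from all causes".

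Other sections bear on how these are analysed:
- Synopsis, Efficacy Analysis: success or failure on any primary or secondary endpoint is summarised against Control.
- Section 10.3: mean differences between arms are judged by a 95% CI, and missing data are neither estimated nor carried forward. Death is not mentioned.
- Section 10.1: no statistical analysis plan will be written.

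**The concern.** Death prevents or cuts short each of the first five outcomes. A patient who dies on the ventilator has no extubation time, cannot be re-intubated or re-admitted to the ICU, and stops accruing ICU and hospital days. Unless the plan says how such a patient is scored, the analyst must choose after the data are in, and the choices can point in opposite directions.

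The either-or rule adds to this. If one item can be met by dying, and one item is enough, the group no longer measures improvement. It is also unclear what is being scored. A reduction in ICU or hospital days has no reference value for a single patient, so it reads as a comparison between arms; freedom from re-intubation reads as a patient-level status. The synopsis phrase on meeting any endpoint can mean any one or each.

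The two mortality wordings matter because a cardiopulmonary restriction and an all-cause count can give different numbers of deaths. In an arm of 10, one death classified differently moves the rate by 10 percentage points.

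**Working it through.** The plan gives no figure for these items, so there is nothing to reproduce. From the documents: mortality of 22% to 62% in the critically ill (Section 2.1), 10 patients per arm (Section 3.3) and follow-up to Day 28. Re-intubation rates, lengths of stay and the 50% v 30% mortality split below are assumptions, chosen for illustration.

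**Will deaths occur?** Expected deaths per arm are 10 × 0.22 = 2.2 to 10 × 0.62 = 6.2. The chance of at least one death in an arm is 1 − 0.78^10 = 91.7% at the low end and over 99.9% at the high end. A scoring rule will be needed.

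**Re-intubation item.** Let m be mortality, with all deaths before extubation and all survivors extubated, and r the re-intubation rate among those extubated.
- Literal item: 1 − (1 − m)r
- Item requiring extubated, alive and not re-intubated: (1 − m)(1 − r)

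| r | m | Literal | Extubated, alive, not re-intubated |
|---|---|---|---|
| 10% | 50% | 95% | 45% |
| 10% | 30% | 93% | 63% |
| 20% | 50% | 90% | 40% |
| 20% | 30% | 86% | 56% |

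On the literal wording, the arm with fewer deaths looks 2 to 4 points worse. On the defined wording it looks 16 to 18 points better. If half the deaths follow extubation, the literal gap is 1 to 2 points (92.5% v 91.5% at r = 10%; 85% v 83% at r = 20%).

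**ICU days counted to death or discharge.** Let d be mean days to death and s mean survivor stay, equal in both arms except that survivors on Active leave k days sooner. Then

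Active − Control = (mC − mA)(s − d) − (1 − mA)k

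With mC = 50%, mA = 30%:
- d = 8, s = 18, k = 0: 0.2 × 10 = +2.0 days (15.0 v 13.0), so the arm with fewer deaths looks worse.
- d = s, k = 0: zero.
- d = 22, s = 14, k = 0: 0.2 × (−8) = −1.6 days.
- d = 8, s = 18: the effect is cancelled at k = 2.0 / 0.7 ≈ 2.9 days.
- With equal mortality and equal stays there is no effect.

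**ICU days in survivors only.** With s = 18 for everyone, the arms agree. But if the extra 20% who survive on Active stay 24 days, the survivor mean is (50 × 18 + 20 × 24) / 70 = 19.7 v 18 days. This shows the selection: the survivors in the two arms need not be comparable patients.

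**Days alive and out of the ICU to Day 28, death scored 0** (d = 8, s = 18): 0.7 × 10 = 7.0 v 0.5 × 10 = 5.0, in favour of the arm with fewer deaths.

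**The case against.** The strongest reply is that being free from re-intubation presupposes extubation, and that no sensible analyst would credit a death on the ventilator. That is a fair guess at intent, but the wording requires neither extubation nor survival, and no other document will supply the rule. It is also fair that the literal error is small: 2 to 4 points is 0.2 to 0.4 of a patient per 10. Under the assumptions above, binomial calculation gives the lower-mortality arm a strictly lower literal count in only 36% (r = 10%) to 47% (r = 20%) of trials.

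A reader might infer several stronger things that the documents do not support:
- **That the composite sits near its ceiling in both arms.** This needs per-patient scoring, which the plan does not state. If the items are judged between arms, there is no per-patient composite.
- **That ICU days are biased against an effective drug.** The direction depends on stays that the documents do not give. Section 2.2.5 hopes for earlier weaning from the ventilator, which could offset the effect, and Section 2.1 says inhaled prostacyclin has not been associated with improved mortality.
- **That a survivors-only comparison is unbiased.** That holds only if the survivors in each arm are alike.
- **That the primary endpoint ignores death.** Death on the ventilator by Day 10 is naturally an inability to extubate (Section 6.1). Death after extubation is not named, but the haemodynamic, vasopressor or oxygenation components may capture some such patients. How often this arises cannot be estimated.
- **That deaths are hidden.** Day-28 mortality, SAEs, the disposition form and individual listings all show them.

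It also stands that these are secondary endpoints in an exploratory study with no formal sample size, and that both mortality wordings mention all causes. Visible deaths do not, however, define the other five items.

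**Conclusion.** The point holds as a gap in endpoint definition that should be fixed. Three parts rest on the text alone: five items lack a rule for death, any one of six is enough without a stated unit of scoring, and mortality has two wordings within the same protocol version. That scoring will matter follows from the cited mortality, with at least a 91.7% chance of a death in each arm.

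The size and direction of any distortion are not established. The +2.0 ICU days, and the change from 2 to 4 points worse to 16 to 18 points better on re-intubation, show what the wording permits under assumed stays, re-intubation rates and a 20-point mortality difference; they are not predictions. The consequence is limited to interpretation of the secondary clinical results.

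**What to change.** 1. Report the six items separately in place of the either-or rule, and state which are scored per patient and which compare arms.
2. Define the re-intubation item as extubated, alive and not re-intubated by Day 28. State how death counts for ICU re-admissions.
3. Compare ICU-free and hospital-free days to Day 28 with death scored 0, showing survival and survivors' days beside them. Treat death before extubation as a competing event for time to extubation.
4. Use all-cause Day-28 mortality in the synopsis, Section 6.2 and Section 10.6.2.
5. Confirm that the data collection form captures dates of extubation, re-intubation, ICU and hospital discharge and ICU re-admission to Day 28. The form is not supplied, and the Day-28 list in Section 9.1.3 names only AEs/SAEs, mortality and concomitant medications, so capture should be checked, not presumed absent.

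Naming death by Day 10 as a primary failure is optional, for the reasons given under the objection. The minimum acceptable change is one line per item saying how death counts, plus one mortality definition.

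The cost is a protocol amendment (Section 11.2.1, with IRB approval where scientific quality or scope is affected), minor programming, and added date capture if it proves missing. No extra patients are needed. Free days mix survival with speed of recovery, which is why the components must be shown. Power stays low: in simulations with assumed stays, a rank-sum test on ICU-free days at 10 per arm has about 9% to 11% power for a 20-point mortality difference.
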